10.3.3. Early Termination Assessments

In case of early termination, the following assessments shall be performed:

- Record date and time of withdrawal
- Record responses to pain assessment:
 - Pain intensity scores on the Numeric Rating Scale (NRS) measured as “How much pain are you experiencing right now?”
 - Pain intensity scores (using the NRS) measured as “What was your worst pain in the last 24 hours?”
 - Pain intensity scores (using the NRS) measured as “What was your average pain in the last 24 hours?”
- Remind to return the e-diary (if applicable)
- Final phone call for safety

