13.1.2. Subject Satisfaction with Postsurgical Pain Control

Subject satisfaction with pain management using 1 question from the International Pain Outcome (IPO) questionnaire will be recorded at 96 hours (± 3 h) post-surgery. (see Appendix 2, [Section 18.2](#)).

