6.1.4. Postsurgical Breakthrough Pain Medication

All opioid and other analgesics (pain medications) administered post-surgery through POD 14 will be recorded. Analgesics will be administered based on the pain assessment as outlined below.

- For the initial treatment of post-surgical pain, subjects may receive either acetaminophen or NSAIDs without exceeding the maximum daily dose.
- If the initial pain treatment (acetaminophen or NSAIDs) is insufficient for pain relief, immediate release PO oxycodone may be administered in a stepwise approach:
 - Initial dose of 5 mg oxycodone may be offered;
 - If the initial opioid dose is insufficient for pain relief, 10 mg oxycodone may be offered.

• If a subject is unable to tolerate PO medication or the PO oxycodone pain relief is insufficient, IV morphine (initiated at 2 mg) or hydromorphone (initiated at 0.2 mg) may be administered.

Post discharge, the subject will be provided with a prescription for oxycodone 5 mg. The subject may take acetaminophen, NSAIDs, or the prescribed oxycodone and will be given instructions on which medication to take PRN based on their pain intensity.

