9.2. Handling Missing Values

9.2.1. Total Post-Surgical Opioid Consumption

For the calculation of the total postsurgical opioid consumption 0-96 hours, both opioid pain medication before hospital discharge and opioid pain medication in the daily diary after discharge will be included. If opioid is taken on the start of study drug administration day but time is missing, time will be imputed as end time of surgery plus (+1) 1 minute. If opioid is taken after the day of study drug administration and time is missing, it will be imputed as 00:00.

For the calculation of the total dose through 96 hours, if a subject's last follow-up time is 96-x hours, then the opioid that was taken between 96-2x hour to 96-x hour will be used to project the amount from the last follow-up time to 96 hours, where time of last follow-up will be defined as the latter of (1) the last NRS pain assessment, (2) the start time of the last opioid pain medication, (3) time of the subject completion of the 96-hour satisfaction questionnaire, and (4) time of last sensory and motor block assessment.

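### The 0–96 h opioid projection is triggered by the last assessment or dose, not by the end of opioid recording, so it can add a dose to a completer whose record is already complete

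*SAP*

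**What the plan says.** SAP 9.2.1 completes the 0–96 h opioid total by extrapolation. When last follow-up falls at 96−x h, "the opioid that was taken between 96-2x hour to 96-x hour will be used to project the amount" for the remaining x hours. Last follow-up is the latest of four times. The list opens with a pain score: "time of last follow-up will be defined as the latter of (1) the last NRS pain assessment". Its second entry is a dose time, "2) the start time of the last opioid pain medication". The remaining two are other assessments: "3) time of the subject completion of the 96-hour satisfaction questionnaire, and (4) time of last sensory and motor block assessment".

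Other provisions bear on this:

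- **Opioid recording.** SAP 6.1.4: "All opioid and other analgesics (pain medications) administered post-surgery through POD 14 will be recorded". For the 0–96 h total, SAP 9.2.1 itself says that "opioid pain medication in the daily diary after discharge will be included".
- **Timing of the 96 h assessments.** Under Protocol 13.1.2 the satisfaction "questionnaire will be recorded at 96 hours", with a window of ±3 h. Protocol 12.1 gives the 96 h current-pain score the same window, and SAP Section 5, Table 3 accepts scores from after 93 h to 99 h.
- **Block tests.** Done in Cohort 1 only, and stopped once offset is confirmed on two consecutive assessments (SAP 6.3.2).
- **Discharge.** After the 168 h assessments in Cohort 1 and the 96 h assessments in Cohort 2 (Protocol 13.8).
- **Daily NRS.** Worst and average pain are scored once a day to POD 14 (SAP 6.1.1).
- **Early termination.** Protocol 10.3.3 requires sites to "Record date and time of withdrawal".

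The total is the first secondary endpoint, second in the test hierarchy (SAP 9.5). It is analysed as ln(OMED), with 3.75 mg assigned to non-users (SAP 9.5.2.1).

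**The concern.** Extrapolation is meant for time over which opioid use is unknown. The four listed times show when a subject was last assessed or last dosed, not when opioid recording ended. A completer may validly have the final pain score and questionnaire at 93 h, while doses continue to be recorded well past 96 h. For that subject, use between the last listed time and 96 h has been observed.

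Item (2) makes this sharper. Because the last opioid start is in the list, the rule can fire only when no opioid is recorded between last follow-up and 96 h. For a completer that is a recorded zero, and any projected dose overwrites it. The error for the subject can therefore only be upward.

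Firing also depends on events after treatment. A recorded opioid after 96 h, or a block test still being done after 96 h, switches the projection off. At stake is the derivation of a hierarchically tested endpoint, and whether two programmers would obtain the same total from the same record.

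**Working it through.** The plan gives no figure for this rule, so there is none to reproduce. The rule can be applied directly.

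**Inputs.** Oral oxycodone has an OMED factor of 1.5 (SAP Table 5), so 5 mg is 5 × 1.5 = 7.5 mg OMED. The earliest valid 96 h assessment is at 93 h, so x is at most 3 h in a compliant completer.

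**Rule.** L = latest of the four times. If L < 96, then x = 96 − L, and doses from 96−2x to 96−x (taken as including both ends) are added once more.

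**Worked cases**, all completers, 5 mg doses, item (1) read as current pain unless stated, no block test after the assessment shown:

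| Case | L (h) | Look-back (h) | Recorded (mg) | Analysed (mg) |
|---|---|---|---|---|
| (a) Assessed 93 h; only dose at 91.5 h | 93 | 90–93 | 7.5 | 15 |
| (b) Assessed 93 h; eight doses, last at 91.5 h | 93 | 90–93 | 60 | 67.5 |
| (c) Assessed 94 h; doses at 50 h and 95 h | 95 | 94–95 | 15 | 22.5 |
| (d) As (a), plus a dose at 110 h | 110 | none | 7.5 | 7.5 |
| (e) As (a), but assessed at 96.5 h | 96.5 | none | 7.5 | 7.5 |
| (f) As (a), with daily NRS counted (e.g. at 107 h) | 107 | none | 7.5 | 7.5 |

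Log-scale shifts: (a) ln(15/7.5) = 0.69; (b) ln(67.5/60) = 0.12; (c) ln(22.5/15) = 0.41. In (c) the dose that sets L is itself repeated. The unscheduled NRS required just before that dose does not change this.

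**How often, on average.** The documents give neither late dosing rates nor actual assessment times, so both are assumed: random 5 mg doses at one per 24, 12 or 6 h.

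1. *No opioid after 96 h, last assessment uniform over 93–99 h.* The rule fires in 3/6 = 50% of completers, but most firings add nothing. A dose is added in 5.7%, 10.7% and 18.5% at the three rates, and the mean rises by 0.45, 0.87 and 1.60 mg OMED. A separate simulation ignoring any opioid after 96 h gave 5.6%, 10.4% and 18.6%, with the geometric mean up about 1.3%. With every last assessment before 96 h (uniform over 93–96 h), that simulation gave 12–37% and 2.6–2.7%.
2. *Item (2) covering all recorded opioids, as written.* Dosing was assumed to stop at a time uniform over 72–96 h or 48–144 h, or to continue to POD 14, with last assessment uniform over 93–99 h or 93–96 h. A dose was added in 0–3.4% of completers, and the geometric mean rose by 0–0.6%.

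**Direction between arms.** Take scenario 1 and let the same rates run for 24 h past 96 h. The chance of no dose in 96–120 h is e^(−24 × rate), that is e^−1, e^−2 and e^−4. The shares become 5.7% × 0.368 = 2.1%, 10.7% × 0.135 = 1.4% and 18.5% × 0.018 = 0.3%. The ordering by dosing rate reverses.

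**The case against.** **Which NRS counts.** Item (1) refers to NRS assessments without restriction, and SAP 6.1.1 lists the daily worst and average scores among them. On that reading a completer with any diary score after 96 h gets no projection, as in case (f). The rule also sits under the heading on missing values, which suggests it is aimed at incomplete subjects. This stands as a possible reading. It would leave the questionnaire and block-test items nearly redundant for completers, though a latest-of list may be redundant. The text settles neither reading, and the same record could yield 7.5 or 15 mg.

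**Whether no entry means no opioid.** In Cohort 2, discharge may precede 96.0 h, and the documents do not show that the diary captures a positive statement of no opioid use. That is fair, but SAP 9.2.1 already takes diary records as the source after discharge, and the POD 14 call asks about medication not entered (Protocol 13.11). In Cohort 1 the subject is still in the facility.

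**Bias toward EXPAREL.** A reader might infer that the rule adds more to the arm with more late opioid use, or with earlier block offset, and so favours EXPAREL. The documents do not support this. Continued use after 96 h switches the rule off, so heavier users can gain less. On the log scale an added dose moves a small total more than a large one: 0.69 in case (a) against 0.12 in case (b). No calculation here models block duration or treatment arm.

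**Frequency.** A reader might also take 6–18% as the expected share. It needs no opioid use after 96 h, and falls to 0–3.4% in the scenarios where item (2) applies as written.

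**Conclusion.** The point holds as a minor defect of definition. SAP 9.2.1 never refers to the end of opioid recording and does not exempt completers. A false dose is added only when all of these hold:

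- item (1) means the current-pain score;
- all applicable listed times are before 96.0 h;
- an opioid was taken in the look-back, at most 3 h long for a compliant completer.

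The error can double one subject's total but is small on average. About 0–3% of completers are affected with item (2) taken at its word, and roughly 6–18% with no opioid after 96 h and last assessments uniform over 93–99 h; a larger share needs assessments concentrated before 96 h. These rates rest on assumed dosing and timing. No change in the trial's conclusion has been shown. The reason to act is that the plan replaces recorded data with imputed data in a hierarchically tested endpoint, on a trigger that depends on post-treatment events.

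**What to change.** In SAP 9.2.1, apply the projection only to subjects who withdrew or were lost to follow-up, so that opioid recording stopped, before 96.0 h. Set last follow-up to the recorded date and time of withdrawal or last contact. For all other subjects, sum the recorded doses to 96.0 h with no projection. In case (a) the total then stays at 7.5 mg.

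Last follow-up should not be defined as the time of the last medication taken. A completer whose last dose was at 80 h would then have x = 16 h and a look-back of 64–80 h, which recreates the fault on a larger scale. If the four-item list is kept for any purpose, state which NRS assessments item (1) covers.

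The cost is one SAP sentence and one derivation change. Withdrawal time is already required by Protocol 10.3.3. The eCRF is not among the documents, so the sponsor should confirm that time of last contact is available for subjects lost to follow-up.

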9.2.2. NRS Pain Intensity Scores

Pain scores obtained during the opioid medication window will be replaced with the worst observation carried forward (wWOCF). For this study, the prescribed opioid pain medication

is oxycodone. However, morphine, hydromorphone, or other opioids may be used. The durations of the analgesic effect for various opioids are listed in Table 6.

· · · · · · · · · · · · · · · · · · ·	Route	Window Used to		
Medication		Replace NRS		
Oxycodone, Oxycocet, Percocet, acetaminophen-	PO, IM, IV, SC	6 hours		
oxycodone, Oxycontin				
Morphine	IV, PO, SC	4 hours		
Hydromorphone (Dilaudid), Hydromorphone	IV	2 hours		
hydrochloride				
Hydromorphone (Dilaudid), Hydromorphone	PO, IM, SC	4 hours		
hydrochloride				
Hydrocodone	РО	6 hours		
Fentanyl	IV, PO, IM	6 hours		
Hydrocodone combination product - Vicodin, Norco,	PO	6 hours		
Lorcet, Lortab, hydrocodone-acetaminophen				
Codeine combination product - Tylenol 3,	РО	6 hours		
acetaminophen-coedine, Paracetamol Forte, Tylenol 4				
Ultram, Tramadol, Tramacol hydrochloride	РО	6 hours		
PO = oral, IV = intravenous, IM = Intramuscular, SC = subcutaneous.				

Table 6: Opioid Pain Medication Window

If other opioid pain medications not listed above are given, the window will be determined prior to the database lock and unblinding. If a combination opioid product is given, the window will be determined by the opioid part of the medication.

For the primary efficacy endpoint of AUC of NRS pain score 0-96 post-surgery, after applying the visit windows (Section 5 Table 3) and wWOCF to all scheduled/unscheduled pain scores, remaining missing data at each scheduled time point (6 h, 12 h , 18 h, 24 h, 30 h, 36 h, 42 h, 48 h, 54 h, 60 h, 66 h, 72 h , 78 h, 84 h, 90 h, and 96 h) will be imputed using the Rubin's (1987) multiple imputation procedure. This procedure replaces each missing value with a set of plausible values that represent the uncertainty about the right value to impute. The procedures of wWOCF and multiple imputation are described in the order as follows.

A. For subjects who take an opioid pain medication, their NRS scores recorded within the window of controlled type of opioid medication (see Table 6) will be replaced by the 'worst' observation. The worst observation will be the highest NRS score from the end of previous opioid window (excluding the exact end of the window) or the end of surgery whichever is later. The NRS score at the time of opioid pain medication

administration will be included in this calculation. Note (1) the NRS score in the window that is higher than the worst value to be carried forward, this "higher" value will not be overwritten. Instead, the worst value will be replaced by this "higher" value and continue carrying forward until the end of the window. (2) if the scheduled NRS score within the window is missing, it will be imputed with this worst value.

B. After the wWOCF imputation described above, if there are still missing NRS scores at scheduled time points, they will be imputed using the multiple imputation procedures using the Markov Chain Monte Carlo (MCMC) method (Schafer 1997). This imputation will be carried out within each treatment group using SAS PROC MI. Thirty imputations will be conducted. To minimize the effect of data skewness on the imputation result, the NRS score is log-transformed [y=log(x+0.5), where y is the transformed score, x is the raw NRS score, and constant 0.5 is added to avoid log(0)] prior to the imputation and back-transformed after the imputation. In order to achieve the stationary distribution and to avoid dependency within samples generated by MCMC method, the number of iterations for the burn-in period will be set to 2000 and the number of iterations between two consecutive samples will be set to 1000.

For the imputed NRS scores, the associated time will be assigned with the exact scheduled time, eg, 48.0 h.

To better simulate the observed NRS pain score, all imputed scores will be rounded to become a number between 0.0 and 10.0 with 1 decimal place.

- C. The AUC at various time intervals will be derived as described in Section 9.5.1 from the imputed NRS scores. For each subject, there will be 50 sets of AUC from the 50 imputed data sets.
- D. The endpoints derived in Step C will be analyzed as described in Section 9.5.1 for each imputed data set.
- E. Rubin's (1987) synthesizing procedure will be applied to synthesize analysis results from the 50 imputed data sets. SAS PROC MIANALYZE will be used for this analysis. The least squares mean (LSM) and standard error (SE) for each treatment group, and the LSM, SE, 95% CI and p-value for the between treatment difference in AUC will be computed from this analysis.

The SAS pseudo-code for multiple imputations and analysis is as follows.

** Step (b) uses MCMC method to create fully imputed data sets

** Note the value for the random seed is fixed to be 156799 so that the results are reproducible, MIN=0 and MAX=10 are to bound the imputed VAS score within 0-10, ROUND=0.1 is to round the imputed NRS score with 1 decimal place. The Box-Cox transformation is to reduce the skewness of the data distribution **

```
proc mi data=adef seed=156799 nimpute=50 out=output_step1 min=0
max=10 round=0.1 minmaxiter=10000;
```

```
by treatment;
mcmc chain=multiple impute=full initial=em prior=jeffreys
nbiter=2000 niter=1000;
var t6 t12 t18 t24 t30 t36 t42 t48 t54 t60 t66 t72 t78 t84 t90
t96 ;
transform boxcox (t6 t12 t18 t24 t30 t36 t42 t48 t54 t60 t66
t72 t78 t84 t90 t96 / c=0.5 lambda=0) ;* this is log(t+0.5)
transformation ;
```

```
run;
```

** Step (c) calculates AUC for each subject in the imputed data set (with _IMPUTATION_ =1 to 50) **;

** Step (d) analyzes AUC using ANCOVA model for each imputed data set and derives LSM, SE for each treatment group and LSM, SE, and 95% CI for the between treatment difference **;

```
ods output Diffs=diff LSMeans=lsm ;
proc genmod data=auc1;
    by _imputation_;
    class trtpn siteid;
    model aval=trtpn siteid age height / dist= normal
    link=identity;
    lsmeans trtpn / diff cl alpha=0.05 ilink;
    ods output LSMeans=lsm;
    ods output Diffs=diff;
```

run;

```
** Step (e) synthesizes LSMs and SEs derived from the 50 imputed data sets **;
ods output ParameterEstimates=lsmdif;
proc mianalyze data=diff alpha=0.05;
    modeleffects estimate;
    stderr stderr;
run;
ods output ParameterEstimates=lsmeans;
proc mianalyze data=lsm alpha=0.05;
    by trtpn;
    modeleffects estimate;
    stderr stderr;
run;
```

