9.5. Efficacy Analysis

For Primary and Secondary Efficacy Analyses, descriptive statistics that are appropriate for the efficacy variable will also be shown by surgical type, but no statistical analyses will be performed within a surgery type. All efficacy analyses will be performed using the Efficacy analysis set.

Unless specified otherwise, all confidence interval will be 2-sided with 95% confidence. All statistical comparison will be 2-sided at alpha=0.05 level. The leading statistical comparison is between EXPAREL and 0.25% bupivacaine HCl for the primary and first two secondary endpoints and between EXPAREL and EXPAREL admixed with 0.25% bupivacaine HCl for the third and fourth secondary endpoints, though all 3 pairwise comparisons (EXPAREL vs 0.25% bupivacaine HCl, EXPAREL vs EXPAREL admixed with 0.25% bupivacaine HCl, and EXPAREL admixed with 0.25% bupivacaine HCl, and EXPAREL admixed with 0.25% bupivacaine HCl, will be presented.

To control for the overall Type-I error rate for the multiple comparisons, the statistical tests will be conducted in the hierarchical order as follows. See also Section 8.1 for detail.

- 1. Primary endpoint: EXPAREL vs 0.25% bupivacaine HCl
- 2. First secondary endpoint: EXPAREL vs 0.25% bupivacaine HCl
- 3. Second secondary endpoint: EXPAREL vs 0.25% bupivacaine HCl
- 4. Third secondary endpoint: EXPAREL vs EXPAREL admixed with 0.25% bupivacaine HCl

5. Fourth secondary endpoint: EXPAREL vs EXPAREL admixed with 0.25% bupivacaine HCl

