9.5.1. Primary Efficacy Endpoint

The primary efficacy endpoint is AUC of the NRS pain intensity scores from 0 to 96 hours postoperation using Efficacy Analysis Set. The NRS pain intensity score is collected from the assessment "How much pain are you experiencing right now?" The worst and average daily pain scores are not included in the AUC calculation.

AUC curve is derived using the trapezoidal rule (see formula below) on the pain scores adjusted for opioid pain medication using the observed and imputed values (see Section 9.2.2). AUC will start with the first pain assessment obtained after surgery (arrival at PACU) and use all subsequent pain assessments up to 96 hours post-surgery. Pain scores collected prior to the opioid medication administration or unscheduled are also included in the AUC calculation. Exact assessment time will be used in deriving AUC.

$$AUC = \left\{ \sum_{i=2}^{n} (p_i + p_{(i-1)})(t_i - t_{(i-1)}) \right\} / 2$$

Where p_i is the NRS pain score at time *i* and t_i is the time, in hours, from end of surgery. Note t_i is pain score collected upon PACU arrival. It is the first time NRS score is collected.

In calculating AUC_{0-96} , if the exact 96-hour pain score is not collected, it will be interpolated using the two nearest before and after data points. If the last 96-hour assessment is before 96.0 hours, then the exact 96-hour pain score for the AUC calculation will use this last observation carried forward.

 $AUC_{0.96}$ for pain intensity from 0 to 96 hours will be summarized by treatment group, by surgery type and overall.

Tests for the superiority of treatment effect of EXPAREL versus 0.25% bupivacaine HCl will be based on the following null hypotheses and alternative hypotheses using the Efficacy analysis set and multiple imputation method:

H_o: EXPAREL is not different from 0.25% bupivacaine HCl with respect to AUC for pain intensity

HA: EXPAREL is superior to 0.25% bupivacaine HCl with respect to AUC for pain intensity

A two-sided hypothesis test will be performed at 5% level of significance comparing EXPAREL and 0.25% bupivacaine HCl as follows:

If the upper bound of the 2-sided 95% confidence interval for the least square (LS) means for the difference of AUC₀₋₉₆ (EXPAREL) – AUC₀₋₉₆ (0.25% bupivacaine HCl) is ≥0, then superiority of EXPAREL to 0.25% bupivacaine HCl is not achieved.

• If the upper bound is <0 then declare that the superiority of EXPAREL to 0.25% bupivacaine HCl is achieved.

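### The SAP 9.2.2 code for the primary analysis pools all pairwise contrasts as one parameter and, once that is repaired, would probably still give an interval somewhat narrower than the ANCOVA it names

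*SAP*

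**What the plan says.** SAP 9.2.2 gives pseudo-code for the primary analysis. The comment on step (d) says that it "analyzes AUC using ANCOVA model for each imputed data set". The code is "proc genmod data=auc1" with "model aval=trtpn siteid age height / dist= normal", an identity link and no scale option. Treatment differences are requested by "lsmeans trtpn / diff cl alpha=0.05 ilink" and saved in a data set called diff.

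Step (e) pools them with "proc mianalyze data=diff alpha=0.05". This call has no BY or WHERE statement and no EDF= option. The next call, which pools the LS means, does have a BY statement on treatment.

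The prose of 9.2.2 (step E) promises an LS mean difference with SE, 95% CI and p-value from this step. SAP 9.5 states "All statistical comparison will be 2-sided at alpha=0.05 level", names EXPAREL against bupivacaine HCl as the leading comparison for the primary endpoint, and adds "though all 3 pairwise comparisons" as results to be presented. SAP 9.5.2.3 reuses the primary model for EXPAREL against the admix arm. The decision rule in SAP 9.5.1 is: "If the upper bound is <0 then declare that the superiority of EXPAREL". It is applied to EXPAREL minus bupivacaine HCl.

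On the number of imputations, step B of 9.2.2 says thirty; steps C and E and the code say 50.

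**The concern.** The primary result is one confidence bound for one contrast, and it opens the testing hierarchy. The code does not isolate that contrast. With three treatment levels, the difference request yields three rows per imputation, and the pooling call treats all rows as repeated estimates of the same quantity. True differences between contrasts are then counted as between-imputation variance.

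A second problem appears once the right rows are selected. An ANCOVA uses the residual mean square RSS/(n-p) and a t distribution on n-p degrees of freedom. If GENMOD estimates the normal scale by maximum likelihood (RSS/n), and MIANALYZE without EDF= takes the complete-data degrees of freedom as infinite, the interval is too narrow on both counts. These are the usual SAS defaults, but the documents do not state them and no SAS was run. Unlike the contrast fault, this one would produce plausible output and could pass unseen.

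**Working it through.** **Inputs.** SD 170, difference 150, 40 per arm and two-sided alpha 0.05 (SAP 10); about 120 subjects in three arms (SAP 4); model terms treatment, site, age and height (SAP 9.2.2). The number of sites S is not given, so 2, 5, 10 and 20 are shown. Few missing scores are assumed.

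**The plan's own figure.** Variance of the difference = 170² × 2/40 = 1445, so SE = 38.0. Power ≈ Φ(150/38.0 − 1.96) = 97.6%. The stated figure of at least 90% is met.

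**Contrast, code run literally with three arms.** Take differences as earlier-coded minus later-coded level, the order EXPAREL, admix, bupivacaine HCl, and admix equal to EXPAREL. The three contrasts are 0, −150 and −150, each repeated over 50 imputations:

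- Pooled estimate = (0 − 150 − 150)/3 = −100.
- Between-row variance = [(100² + 50² + 50²)/3] × 150/149 = 5034.
- Total variance = 1445 + (151/150) × 5034 = 6512, so SE = 80.7.
- Degrees of freedom = 149 × (1 + 1445/5067)² = 246, where 5067 = (151/150) × 5034. The critical value is 1.97 and the 95% CI is −259 to 59.

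The intended contrast gives −150, SE 38.0, 95% CI −225 to −75. With the order EXPAREL, bupivacaine HCl, admix, the literal result is 0 (CI −255 to 255). In simulations at the design effect with 5, 10 and 20 sites, the literal code (first order) declared superiority in about 5% of trials, against about 95 to 97% for the correct ANCOVA. Under the null it rejected in about 0%.

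**Standard error and degrees of freedom, contrast isolated, SAS defaults assumed.** p = arms + (S − 1) + 2 and df = n − p.

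- SE factor = √(df/n).
- Level, both effects = 2·P(t_df > 1.96·√(df/n)).
- Level, scale only = 2·P(t_df > t_.975,df·√(df/n)).
- Level, missing EDF= only = 2·P(t_df > 1.96).
- Correct CI width relative to coded width = t_.975,df / (1.96·√(df/n)).

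| n (arms) | Sites | p | df | SE factor | Scale only | EDF= only | Both | CI ratio |
|---|---|---|---|---|---|---|---|---|
| 120 (3) | 2 | 6 | 114 | 0.975 | 5.60% | 5.24% | 5.86% | 1.037 |
| 120 (3) | 5 | 9 | 111 | 0.962 | 5.93% | 5.25% | 6.20% | 1.051 |
| 120 (3) | 10 | 14 | 106 | 0.940 | 6.52% | 5.26% | 6.83% | 1.076 |
| 120 (3) | 20 | 24 | 96 | 0.894 | 7.90% | 5.29% | 8.28% | 1.132 |
| 80 (2) | 2 | 5 | 75 | 0.968 | 5.75% | 5.37% | 6.16% | 1.050 |
| 80 (2) | 5 | 8 | 72 | 0.949 | 6.26% | 5.39% | 6.71% | 1.072 |
| 80 (2) | 10 | 13 | 67 | 0.915 | 7.22% | 5.42% | 7.74% | 1.113 |
| 80 (2) | 20 | 23 | 57 | 0.844 | 9.64% | 5.49% | 10.35% | 1.210 |

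At n = 120 the design SE of 38.0 would be reported as 37.1, 36.6, 35.7 or 34.0. The chance of a false superiority claim is half the two-sided level: 2.9, 3.1, 3.4 or 4.1% instead of 2.5%.

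A simulation of 100,000 null trials per case agrees. Both effects together gave 5.8, 6.2, 6.9 and 8.3% at n = 120, and 6.2, 6.9, 7.7 and 10.5% at n = 80. The correct ANCOVA t-test gave 4.95 to 5.13%.

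**The case against.** The code is labelled pseudo-code and is visibly a sketch: step (c) is only a comment, and the analysis data set is never built. SAP 9.5 and 9.5.1 name the right contrast and sign, so a programmer would probably see that three rows per imputation are being pooled. This stands, and it limits the practical risk of the contrast fault. It does not help with the scale or the degrees of freedom, where nothing would look amiss.

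Part of SAP 9.5.1 is not in the copy reviewed. SAP 9.5.2.1 and 9.5.4 cite that section for two excluded subjects, a sensitivity analysis and the model specification, none of which is in the visible part. Fuller model text may therefore exist, and one cannot say that the plan has no other specification. It would still have to be reconciled with this code.

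A reader might infer that the planned primary test, as written, runs above 5% towards a false superiority claim. The documents do not support that. Run literally on three arms, the code almost never rejects under the null. The inflated level needs someone to repair the contrast and leave the rest, and it rests on software defaults that the documents do not state.

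A reader might also infer that the wrong model is fitted. It is not: the terms match the ANCOVA described in SAP 9.5.2.1, so the LS mean differences within each imputation are unaffected.

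**Conclusion.** The concern holds in a limited form. The pseudo-code would not deliver the primary estimate and interval that SAP 9.2.2, 9.5 and 9.5.1 promise.

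The contrast fault is visible in the code itself and is the larger one. It depends on the analysis data set holding all three arms, which SAP 9.5 and 9.5.2.3 suggest but do not state. Its effect is a badly diluted or mis-targeted estimate, and it is likely to be caught.

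The standard error and degrees of freedom matter after that repair. Under the assumed SAS defaults and with few missing scores, the two-sided level is 5.9 to 8.3% at n = 120 for 2 to 20 sites, or 6.2 to 10.4% if only two arms are analysed (n = 80). If GENMOD in fact used the residual mean square, only the EDF= effect would remain (5.2 to 5.5%), which is negligible. The conflict between thirty and 50 imputations is editorial.

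This should be corrected before the analysis is programmed, but it is not evidence that the trial's type I error is uncontrolled as designed.

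**What to change.** - Step (d): fit the model in PROC MIXED or PROC GLM, so that the residual mean square and residual degrees of freedom are used.
- Step (e): sort and pool by contrast, or subset to EXPAREL minus bupivacaine HCl with the sign used in SAP 9.5.1, and set EDF= to the ANCOVA residual degrees of freedom.
- State whether the analysis data set holds three arms or two.
- State 50 imputations throughout SAP 9.2.2.

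The cost is a few words of text and code, with no change to the design, the data collected or the model terms. Relative to the contrast-isolated GENMOD analysis, the CI becomes about 4 to 13% wider at n = 120 (5 to 21% at n = 80), which is its correct width. Simulated power of the corrected three-arm analysis at the design effect is about 94 to 97% for 5 to 20 assumed sites, still above the planned 90%.
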